| SAFETY EVALUATIONS
(PRIMARY OUTCOMES)               | 
Tolerability of pirfenidone: The primary outcome will be the number of subjects that discontinue pirfenidone due to a treatment emergent adverse event (TEAE). A secondary outcome will be the proportion of subjects experiencing a TEAE.
 
Tacrolimus dose change: The outcome will be the ratio of tacrolimus-on-pirfenidone to tacrolimus-off-pirfenidone corrected for the subject's specific steady-state tacrolimus concentration. Subjects with steady-state blood concentration of tacrolimus, as assessed by 10-12 hour trough level, will initiate pirfenidone. Tacrolimus trough level will be measured weekly for the first 6 weeks after starting pirfenidone. Another measurement will be done at week 8. Once a therapeutic blood concentration (8-12 ng/ml) is achieved, measurements will be done monthly. First, we will calculate the concentration-to-dose ratio of tacrolimus on and off pirfenidone by dividing the tacrolimus blood concentration by the corresponding total daily dose of tacrolimus for each period. To obtain the conversion ratio, then we will divide the concentration-to-dose ratio for tacrolimus-on-pirfenidone by the concentration-to-dose ratio for tacrolimus-off-pirfenidone ([blood concentration on pirfenidone/daily dose on pirfenidone]/[blood concentration off pirfenidone/daily dose off pirfenidone]).
 |
| EFFICACY EVALUATIONS                                    | 
FVC decline: We will evaluate change in FVC every 3 months after initiation of pirfenidone.
   |

|   |   |
|---|---|
| (SECONDARY OUTCOMES)             | 
Radiographic progression: We will evaluate fibrosis scores on chest CT at RCLAD onset and in the follow up CT scans performed as part of routine clinical care.
   |
| PLANNED INTERIM ANALYSES         | Quarterly   |
|   |   |

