| Rationale for Number of Subjects | 
This is a pilot study with the primary outcome of determining pirfenidone tolerability and its effect on tacrolimus dosing. Even with a small cohort, we hypothesize we will be powered to detect a significance difference in tacrolimus dosing. Based on the single report of tacrolimus dosing increase of 2.5 fold, and conservatively estimating a standardized effect size of 1 (doubling of tacrolimus dose and a standard deviation of the change of 50%), a sample of 8 subjects would be required to detect a significant difference, assuming a two-sided <math>\alpha</math> of 0.05 and <math>\beta</math> of 0.20.
 |
|   |   |

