## 4 STUDY DESIGN

### 4.1 Study Overview

1) We will screen for eligible subjects using the computer algorithm on spirometry data abstracted from Apex monthly and by suggestion of the transplant pulmonologists. 2) Then, we will review CT scans to adjudicate a diagnosis of RCLAD. 3) Finally, our pharmacist will determine if tacrolimus dose is stable. After these 3 steps are completed subjects will be eligible for the study.

Subjects will be recruited at their transplant clinic visit or by phone if they previously consented to be contacted with new research study opportunities. We will seek to enroll ten subjects, who will receive pirfenidone for 52 weeks, titrated to 2403 mg/day (3 capsules, 3× daily) over a period of six weeks. Genentech has agreed to provide study drug free of cost.

TEAE will be recorded and graded according to the Common Terminology Criteria for Adverse Events (CTCAE) v3.0^21. Our study coordinator will contact subjects by phone every 2 weeks for the first 6 weeks to inquire about TEAE and then monthly. Subjects will be provided a phone number to report any additional TEAE. A Data Safety Monitoring Board will be convened.

As part of their routine post-transplant surveillance, subjects have monthly laboratory testing that includes tacrolimus blood concentration and liver function tests. Therefore, the manufacturer recommendations of monitoring liver function tests monthly for the first six months and then every 3 months while taking Pirfenidone, will be followed.

Subjects will continue their routine care with clinic visits, spirometry and CT as clinically indicated. In our clinical practice, subjects with RCLAD are expected to have a clinic visit and spirometry approximately every 3 months and a CT scan every 6 to 12 months.

If RCLAD subjects in the study undergo bronchoscopy for a clinical indication, bronchoalveolar lavage, biopsies, airway brushes and plasma specimens will be collected in the biorepository for future analysis of changes in pro-fibrotic mediators after initiation of pirfenidone. These specimens will be collected as part of the ongoing "Lung Transplantation: Improving outcomes through the development of a clinical database and biorepository" study number 13-10738. In the future, we plan to explore whether subjects with RCLAD have a greater rate of decline in telomere length in airway epithelial cells compared subjects without RCLAD.

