## 8 STATISTICAL METHODS AND CONSIDERATIONS

Prior to the analysis of the final study data, a detailed Statistical Analysis Plan (SAP) will be written describing all analyses that will be performed. The SAP will contain any modifications to the analysis plan described below.

**Interim analysis plans:** We will plan interim analyses of data quality and patient compliance on a quarterly basis to insure adequate study conduct. Modifications to the study conduct (e.g. changes to the outcome measures, or even cessation of the study if indicated by issues with performance or outcomes) will be considered at each of these analyses.

**Power:** This is a pilot study with the primary outcome of determining pirfenidone tolerability and its effect on tacrolimus dosing. Even with a small cohort, we hypothesize we will be powered to detect a significance difference in tacrolimus dosing. Based on the single report of tacrolimus dosing increase of 2.5 fold, and conservatively estimating a standardized effect size of 1 (doubling of tacrolimus dose and a standard deviation of the

change of 50%), a sample of 8 subjects would be required to detect a significant difference, assuming a two-sided  $\alpha$  of 0.05 and  $\beta$  of 0.20.

**Data analysis plan:** Since we will be comparing within subject changes, we will use paired t-test to compare the tacrolimus-on-pirfenidone to tacrolimus-off-pirfenidone ratio. For analyses involving repeated measures including change in FVC, fibrosis score, and telomere length, we will use mixed effects models including subject as a fixed effect. Slopes before and after the initiation of pirfenidone will be compared.

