## **WITHDRAWAL**

### **Discontinuation of Patients:**

The investigator will discontinue patients from the study drug or the study or both in the following circumstances:

- The patient, for any reason, requires treatment with another therapeutic agent that has been demonstrated to be effective for treatment of the study indication. In this case, discontinuation from the study occurs prior to introduction of the new agent.

- The investigator decides that the patient should be withdrawn from the study. If a serious adverse event or a clinically significant laboratory value is the basis for this decision, the investigator will discontinue the study therapy and take appropriate measures. The investigator must **immediately** notify the study sponsor or its designee.
- The patient or attending physician requests withdrawal of the patient from the study.
- The investigator or the study sponsor stops the study or stops the patient's participation in the study for medical, safety, regulatory, or other reasons consistent with applicable laws, regulations, and good clinical practice (GCP).
- The study therapies have shown unacceptable toxicity.
- The patient becomes pregnant or fails to use adequate birth control (for women with reproductive potential).
- The patient is noncompliant with study procedures.

When a subject withdraws before completing the study, the reason for withdrawal is to be documented in the CRF and in the source document.

Study agents assigned to the withdrawn subject may not be assigned to another subject. Subjects who withdraw will not be replaced.

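### The sample-size statement is inconsistent: its parenthesis implies an effect size of 2, and at the stated effect size of 1 the planned paired t-test needs 10 subjects, not 8, for 80% power

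*Combined protocol and SAP*

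**What the plan says.** The synopsis (Rationale for Number of Subjects) starts from a single report of a 2.5-fold rise in tacrolimus dose. It then assumes, as a conservative figure, a "standardized effect size of 1 (doubling of tacrolimus dose and a standard deviation of the change of 50%), a sample of 8 subjects", at two-sided alpha 0.05 and beta 0.20. Section 8 (Power) repeats the text and the conclusion: "a sample of 8 subjects would be required to detect a significant difference".

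The test is named in section 8 (Data analysis plan): "we will use paired t-test to compare the tacrolimus-on-pirfenidone to tacrolimus-off-pirfenidone ratio". The outcome is defined in the synopsis under safety evaluations: "The outcome will be the ratio of tacrolimus-on-pirfenidone to tacrolimus-off-pirfenidone". It is computed as the concentration-to-dose ratio on pirfenidone divided by the same ratio off pirfenidone.

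On numbers, section 4.1 says "We will seek to enroll ten subjects". The power text makes no allowance for missing data, and the Withdrawal section states: "Subjects who withdraw will not be replaced".

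**The concern.** The effect size and its explanation disagree. On the plain reading of the parenthesis the standardized effect is 2, while the sentence says 1. The number 8 then follows from neither value under the test that will be used: it is too few at an effect size of 1 and more than needed at 2.

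The effect on tacrolimus is a primary objective (section 3.1), and the pilot is meant to supply the groundwork for a multicentre randomized trial. A reader who takes 8 at face value will believe that enrolling 10 leaves two subjects to spare. A designer of the later trial would carry forward an effect size and an SD that do not fit together, with no scale attached to either.

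**Working it through.** **Inputs.** Two-sided alpha 0.05, power 80%, effect size d = 1, doubling of dose, SD of the change 50%, n = 8 (synopsis and section 8); paired t-test (section 8); enrolment 10 (synopsis and section 4.1).

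**1. Reproducing the 8.** The one-sample normal approximation is n = ((z₀.₉₇₅ + z₀.₈₀)/d)². With d = 1 this is (1.960 + 0.842)² = 7.85, rounded up to 8. Under the normal distribution, power at n = 8 is 80.7%. So 8 is the normal-approximation figure at the stated effect size. A one-sided t-test also gives 8 (7.73, rounded up), but that contradicts the stated two-sided alpha.

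**2. The planned test at d = 1.** A paired t-test on n differences has n − 1 degrees of freedom and noncentrality d√n. At n = 8 the critical value is 2.365 rather than 1.960, and the noncentrality is 2.83. Exact power, two-sided 0.05:

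| n | d = 1 | d = 1.2 | d = 2 |
|---|---|---|---|
| 4 | 28.9% | 38.3% | 75.5% |
| 5 | 40.1% | 53.0% | 90.9% |
| 7 | 60% | 75.4% | 99.1% |
| 8 | 68.1% | 82.8% | 99.8% |
| 9 | 74.8% | 88.2% | 99.9% |
| 10 | 80.3% | 92.0% | >99.9% |

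At d = 1, solving for 80% power gives n = 9.94, so 10. A simulation of 400,000 trials agrees (68.1% at n = 8, 80.3% at n = 10). The effect detectable with 80% power is 1.16 at n = 8 and 1.00 at n = 10.

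**3. The parenthesis.** How the 50% is read decides the effect size:

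- Dose scale, SD 50% of baseline (the plain reading): doubling 100/50 = 2; the cited 2.5-fold rise 150/50 = 3.
- SD equal to 50% of the doubled dose, that is 100% of baseline: 100/100 = 1.
- On/off concentration-to-dose ratio, assuming an unchanged trough: a doubled dose takes the ratio from 1 to 0.5, so 50/50 = 1; a 2.5-fold rise takes it to 0.4, so 60/50 = 1.2.

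The second and third readings recover d = 1, but the text names neither.

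**4. Does 8 follow from d = 2?** No. The t-test then needs 4.22, so 5 subjects; the normal approximation gives 7.85/4 = 1.96, so 2.

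**The case against.** The strongest reply is that nothing in the design has to change. The figure 8 is a recognized approximation, not a slip. Enrolment is 10, and 10 evaluable subjects give at least 80% power on every reading above. This stands, and it limits the weight of the point.

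The effect size of 1 can also be defended on the on/off ratio, which is the outcome to be tested. But the sentence speaks of dose, so the scale still has to be stated. A log scale, natural for a ratio, would give yet another answer. If one assumes a coefficient of variation of 50%, d is about 1.47; with an SD of ln 1.5 it is 1.71. Eight subjects then have about 94% to 98% power. The documents name no log scale, so this widens the ambiguity and does not settle it.

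It can further be said that withdrawal from the trial is not loss from this endpoint. Troughs are taken weekly for six weeks and again at week 8, and the observational study cited under Stopping Rules reports a median of 99.5 days to discontinuation for an adverse event. That is fair: many who stop will already have supplied an on-treatment value. Some early stoppers may not, and the plan does not say which on-treatment measurement is analysed. The Stopping Rules section expects up to 3 of 10 to discontinue. If all three were lost to this endpoint, 7 subjects at d = 1 would give 60% power; that is a worst case, not a forecast.

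**Conclusion.** The concern holds. At the stated effect size of 1, the claim that 8 subjects give beta 0.20 is not true of the planned two-sided paired t-test: beta is 0.32, a shortfall of about 12 points of power, and 10 subjects are needed. The plain reading of the parenthesis gives an effect size of 2, at which 5 subjects are enough and 8 give 99.8%. The document does not let a reader decide between these cases.

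The practical consequence is confined to the case d = 1: all 10 planned subjects must then be evaluable for the tacrolimus comparison, and the apparent margin of two does not exist. The power figures assume normally distributed within-subject differences; the ratio-scale effect sizes also assume a constant trough. This should be corrected, but it does not call the planned enrolment into question.

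**What to change.** In the synopsis and in section 8 (Power), keep enrolment at 10 and replace the power claim with wording such as: at a standardized effect of 1, 10 evaluable subjects give 80% power for a two-sided 0.05 paired t-test, and 8 evaluable subjects give 68% (detectable effect 1.16).

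Make the parenthesis agree with the effect size. On the dose scale, that means either an SD of 100% for an effect of 1, or an effect of 2 for an SD of 50%. Better, give the assumed mean and SD on the scale that will be tested, the on/off concentration-to-dose ratio. If that scale was meant, the entry would be a mean ratio of 0.5 (a fall of 50%) with SD 0.5. The authors should check that such an SD is credible, because a normal distribution with those values puts about 16% of a positive ratio below zero. If the analysis is to be on the log scale, the SD should be stated there and power recomputed.

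The cost is wording in two places, with no more patients and no change of test. The text would have to admit that, at an effect size of 1, enrolling 10 leaves no allowance for non-evaluable subjects.

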## 1 BACKGROUND

Despite advances in lung transplantation, median survival remains only 55% at 5 years. The primary cause of death is chronic lung allograft dysfunction (CLAD), occurring in 43% of recipients at 5 years. Recently, it has been recognized that CLAD can have an obstructive (BOS) or a restrictive (RCLAD) phenotype, also known as restrictive allograft syndrome (RAS), and that both may coexist. These phenotypes differ not only in their spirometric, radiographic and histologic features but also in their rates of progression and survival (Figure 1). Thus, there is a critical need to find therapies other than re-transplantation, which remains the only effective therapeutic option and explore the pathobiology driving RCLAD.

RCLAD shares features with Idiopathic Pulmonary Fibrosis (IPF), including its progressive and lethal course, extracellular matrix deposition, architectural distortion, fibroblast proliferation, and short telomeres in lung epithelial cells (Fig 2). These common features suggest RCLAD and IPF may share molecular pathogenesis. As a result, some have explored using FDA approved anti-fibrotic medications for IPF in RCLAD in case reports.

## 2 STUDY RATIONALE

This proposal aims to gather the preliminary data needed to design a multicenter randomized controlled trial (RCT) of pirfenidone for RCLAD. To do so, we first need evidence of tolerability, to understand drug interactions with the immunosuppressive regimen used to maintain allograft function and early evidence that pirfenidone may slow FVC decline and radiographic progression in RCLAD.

Evidence that pirfenidone is well tolerated in transplant recipients and that it slows the progression of RCLAD would be paradigm shifting. Further, identifying subjects at risk for RCLAD before the onset of spirometric changes would allow to start therapeutic interventions sooner, maximizing their benefit. Finding biomarkers that predict response to pirfenidone would identify patients most likely to benefit.

## 3 STUDY OBJECTIVES

### 3.1 Primary Objectives

The primary objectives of this proposal are to assess tolerability of pirfenidone and determine its impact on tacrolimus blood concentration.

BOS      RCLAD / RAS

[figure not shown]
[figure not shown]

Fig 1. Restrictive Allograft syndrome (RAS). 3.

We hypothesize that treatment-emergent adverse effects (TEAE) in lung transplant recipients will be similar to subjects with IPF, leading to drug discontinuation in the same proportion of subjects.

Based on available literature, we hypothesize that initiation of pirfenidone will be associated with an increase in tacrolimus dose.

### 3.2 Secondary Objectives

To determine if pirfenidone slows allograft dysfunction in RCLAD as evidenced by a slower FVC decline and/or a slower progression of radiographic findings.

## 4 STUDY DESIGN

### 4.1 Study Overview

1) We will screen for eligible subjects using the computer algorithm on spirometry data abstracted from Apex monthly and by suggestion of the transplant pulmonologists. 2) Then, we will review CT scans to adjudicate a diagnosis of RCLAD. 3) Finally, our pharmacist will determine if tacrolimus dose is stable. After these 3 steps are completed subjects will be eligible for the study.

Subjects will be recruited at their transplant clinic visit or by phone if they previously consented to be contacted with new research study opportunities. We will seek to enroll ten subjects, who will receive pirfenidone for 52 weeks, titrated to 2403 mg/day (3 capsules, 3× daily) over a period of six weeks. Genentech has agreed to provide study drug free of cost.

TEAE will be recorded and graded according to the Common Terminology Criteria for Adverse Events (CTCAE) v3.0^21. Our study coordinator will contact subjects by phone every 2 weeks for the first 6 weeks to inquire about TEAE and then monthly. Subjects will be provided a phone number to report any additional TEAE. A Data Safety Monitoring Board will be convened.

As part of their routine post-transplant surveillance, subjects have monthly laboratory testing that includes tacrolimus blood concentration and liver function tests. Therefore, the manufacturer recommendations of monitoring liver function tests monthly for the first six months and then every 3 months while taking Pirfenidone, will be followed.

Subjects will continue their routine care with clinic visits, spirometry and CT as clinically indicated. In our clinical practice, subjects with RCLAD are expected to have a clinic visit and spirometry approximately every 3 months and a CT scan every 6 to 12 months.

If RCLAD subjects in the study undergo bronchoscopy for a clinical indication, bronchoalveolar lavage, biopsies, airway brushes and plasma specimens will be collected in the biorepository for future analysis of changes in pro-fibrotic mediators after initiation of pirfenidone. These specimens will be collected as part of the ongoing "Lung Transplantation: Improving outcomes through the development of a clinical database and biorepository" study number 13-10738. In the future, we plan to explore whether subjects with RCLAD have a greater rate of decline in telomere length in airway epithelial cells compared subjects without RCLAD.

## 5 SUBJECT SELECTION

### 5.1 Study Population

Subjects with a diagnosis of RCLAD who meet the inclusion and exclusion criteria will be eligible for participation in this study.

### 5.2 Inclusion Criteria

1. Subjects aged 18 to 80 years old who underwent bilateral lung transplantation at UCSF.
2. Diagnosis of RCLAD based on the International Heart and Lung Transplant (ISHLT) classification. The diagnosis of RCLAD is based on spirometry (FEV1 ≤ 80% and FVC ≤ 80% of best post-transplant baseline) and CT scan (e.g. pleuroparenchymal fibroelastosis) findings.
3. Subjects with steady-state blood concentration of tacrolimus, as assessed by 10-12 hour trough level.

[figure not shown]

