## PROTOCOL SYNOPSIS

|                                   |  |
|-----------------------------------|--|
| TITLE                      | PIRFENIDONE FOR RESTRICTIVE ALLOGRAFT DYSFUNCTION (PIRCLAD)   |
| SPONSOR                    | Nina Ireland Program for Lung Health discretionary funds from [name]   |
| FUNDING ORGANIZATION       | UCSF   |
| NUMBER OF SITES            | 1  |
| RATIONALE                  | 
Long-term survival after lung transplant is limited by the development of chronic lung allograft dysfunction. In approximately 30% of cases, chronic lung allograft dysfunction has a restrictive phenotype (RCLAD) characterized by fibrosis with rapid progression. Approximately 60% of patients with RCLAD die within one year from respiratory failure. Currently, there are no therapies available for RCLAD. Due to the similarities between RCLAD and Idiopathic Pulmonary Fibrosis (IPF), there is keen interest in the transplant community to investigate the effect of the anti-fibrotic drug pirfenidone in RCLAD. Pirfenidone has been proved to slow the progression of IPF and is approved by the Food and Drug Administration (FDA) for that indication.
 
This protocol will evaluate the safety and tolerability of pirfenidone in lung transplant recipients with RCLAD. The results of this pilot study will provide the foundation for a multicenter randomized control trial to evaluate the efficacy of pirfenidone in slowing the progression of RCLAD.
 |
| STUDY DESIGN               | Interventional, open-label, pilot study  |
| PRIMARY OBJECTIVE          | Asses the safety and tolerability of Pirfenidone in lung transplant recipients with RCLAD.   |
| NUMBER OF SUBJECTS         | 10   |
| SUBJECT SELECTION CRITERIA | 
Inclusion Criteria:
 
Subjects aged 18 to 80 years old, who underwent bilateral lung transplantation at UCSF and have a diagnosis of RCLAD based on the International Heart and Lung Transplant (ISHLT) classification.
 
The diagnosis of RCLAD is based on spirometry (FEV1 <math>\leq</math> 80% and FVC <math>\leq</math> 80% of best post-transplant baseline) and CT scan (e.g. pleuroparenchymal fibroelastosis) findings.
 
Subjects with steady-state blood concentration of tacrolimus, as
   |

|  |   |
|--|---|

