**Tacrolimus concentration measurement:** Patients will continue to use their chosen laboratory for tacrolimus measurement, as part of their clinical care. As it is our clinical practice, the results will be reviewed daily through Titus and the transplant nurse coordinators will contact the patients with instructions to adjust their tacrolimus dose.

**Liver function test measurement:** Patients will continue to use their chosen laboratory for monthly liver function test measurement according to the post-transplant surveillance protocol. We will track these values every month for the first 6 months of Pirfenidone therapy and every 3 months for the remaining 6 months, following manufacturer's recommendations.

**Office spirometry (FVC):** As part of their clinical care, patients will have office FVC measurement (spirometry) approximately every 3 months or more often if clinically indicated according to ATS/ERS guidelines.

**High-resolution chest CT (HRCT):** Patients will have a HRCT every 6 to 12 months as part of their clinical care. We will review these images to evaluate fibrosis scores.

**Reporting of clinical events:** All patients will be asked to report clinical events (e.g. new or worsening symptoms, unscheduled medical visits, hospitalizations) to the study coordinator over the phone. The study coordinator will ask the transplant nurse coordinators and review the medical record to investigate if any other events occurred.

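### The before/after FVC slope comparison has no known value under no drug effect, so it cannot determine whether pirfenidone slows decline (Sections 3.2, 5.2 and 8)

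*Combined protocol and SAP*

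**What the plan says.** - **Entry.** Section 5.2 requires FEV1 at or below 80% and "FVC ≤ 80% of best post-transplant baseline", plus CT findings. It sets no limit on how long ago the fall occurred.
- **Finding subjects.** Section 4.1: "We will screen for eligible subjects using the computer algorithm on spirometry data abstracted from Apex monthly". Transplant pulmonologists may also suggest subjects.
- **Design.** The synopsis describes an "Interventional, open-label, pilot study" and lists no control product. Section 4.1: "We will seek to enroll ten subjects".
- **FVC data.** The Section 6 schedule places FVC at weeks 8, 20, 32, 44 and 52, and none at or before drug start. Otherwise, "patients will have office FVC measurement (spirometry) approximately every 3 months or more often if clinically indicated".
- **Analysis.** Section 8 says "we will use mixed effects models" for repeated measures, with subject as a fixed effect, and then: "Slopes before and after the initiation of pirfenidone will be compared". It gives no pre-drug window, minimum number of values, rule for the qualifying value or slope structure.
- **Purpose.** Section 3.2: "To determine if pirfenidone slows allograft dysfunction in RCLAD as evidenced by a slower FVC decline".

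**The concern.** A before/after comparison supports a statement about the drug only if the expected change without the drug is known. Here it is not, for two reasons.

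First, subjects are selected on a low FVC relative to a maximum. A value that qualifies is low partly by chance, and a best value is high partly by chance. If those values sit in the pre-drug record, the pre-drug slope tends to be too steep. On-drug values are not selected in this way.

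Second, the natural course need not be a straight line. A window that reaches back before onset makes the pre-drug slope too shallow. Decline that levels off by itself makes the on-drug slope look better.

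Section 8 offers no other analysis of FVC decline for the Section 3.2 objective, and Section 2 wants the result as early evidence for a randomized trial. A false signal of slowing, or a real benefit hidden by the window, would carry into that decision.

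**Working it through.** **Plan's own figure.** There is none for FVC. The only sample-size calculation (8 subjects) concerns tacrolimus.

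**Where the pre-drug slope comes from.** The first scheduled FVC is week 8, so every pre-drug value is a routine clinical one. The screening algorithm reads the same kind of record. That makes it likely, though not certain, that the qualifying value enters the pre-drug slope.

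**Weight of one value.** With visits every 3 months, the least-squares weight of the last value is (t_last - mean t) / sum of (t - mean t)².
- 6-month window, values at 0, 0.25 and 0.5 years: 0.25 / (0.0625 + 0 + 0.0625) = 2 per year.
- 12-month window, five values: 0.5 / (0.25 + 0.0625 + 0 + 0.0625 + 0.25) = 0.8 per year.

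A qualifying value that is 3 points low by chance therefore steepens the pre-drug slope by 6 or 2.4 points per year.

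**Simulation with no drug effect.** From the documents: the 80% threshold, visits about every 3 months, on-drug FVC at weeks 8, 20, 32, 44 and 52, and groups of 10. Assumed, because the documents give no figures: true decline of 10 to 30% of best per year and visit-to-visit SD of 3 or 5% of best. Apparent slowing = 1 - (on-drug slope / pre-drug slope); a negative value is apparent acceleration.

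*6-month window* (qualifying value included, drug started 1.5 months after it; slopes in % of best per year):

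| True decline | SD | Pre-drug | On drug | Apparent slowing |
|---|---|---|---|---|
| 10 | 3 | -16.4 | -10.0 | 39% |
| 10 | 5 | -23.2 | -9.9 | 57% |
| 20 | 3 | -23.4 | -19.9 | 15% |

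Over 10 to 30% decline and SD 3 to 5%, the range is about 6 to 57%. It is smallest when decline is fast and noise is low.

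*12-month window* (stable phase, then linear decline; qualifying value included; drug started at that visit; slopes vary between subjects):

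| True decline | SD | Pre-drug | On drug | Apparent slowing |
|---|---|---|---|---|
| 10 | 3 | -11.494 | -9.995 | 13% |
| 10 | 5 | -13.321 | -10.032 | 25% |
| 20 | 3 | -18.267 | -20.041 | -10% |
| 20 | 5 | -17.349 | -19.879 | -15% |
| 30 | 3 | -20.969 | -29.890 | -43% |
| 30 | 5 | -19.152 | -29.898 | -56% |

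With a common slope and a 1.5-month lag, the last setting gives about -50%. Across such set-ups the range is about -50% to +30%.

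**Other choices the plan leaves open** (on-drug minus pre-drug slope, % of best per year, 12-month window, SD 3 to 5; positive = apparent slowing):
- Linear decline throughout, qualifying value included: +0.8 to +4.4. A paired test with n = 10 falsely finds slowing in 5 to 25% of trials, against a nominal 2.5%.
- Decline that levels off naturally, qualifying value included: +4.1 to +9.4, with a false finding in 52 to 99% of trials.
- Qualifying value dropped (stable phase, 10% decline, SD 3): pre-drug -8.143, on drug -10.037. The bias reverses, because the remaining values are those that had not yet crossed.
- Window wholly after the qualifying value: -0.11 to +0.13 if decline is linear, but +1.2 to +5.4 if it levels off.
- Random-slope model on the full history: slope change of 0.02 and -0.10 under linear decline. With a stable phase before onset, the same model shows a spurious acceleration of about 11 to 23.

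**The case against.** The strongest reply is that the bias comes from how the slope is computed. If decline is linear and the whole FVC history on which entry depends is in a suitable mixed model, it largely disappears. That is correct, and it rules out the inference that selection biases the contrast whatever the model. But the result needs the shape of decline to be modelled correctly, and the plan specifies neither the history nor the shape.

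A reader might also infer more than the documents support:
- *That FVC has just fallen at entry.* Section 5.2 sets no time limit, and physician suggestion can bring in established cases. Monthly screening makes recent falls likely, no more.
- *That the qualifying values do supply the pre-drug slope.* No window is defined, so this is likely but not stated.
- *That the contrast must be non-zero, or must favour the drug.* It can be positive, negative or near zero.
- *That 57% is the typical size.* It needs the slowest assumed decline, the largest noise and a 6-month window. The synopsis describes rapid progression, which points to smaller values with that window.

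CT review, the FEV1 criterion and the exclusion of other causes of FVC decline make a purely chance crossing less likely to lead to entry. They do not remove the noise in the qualifying value. In a simulation over 10 to 20% decline and SD 2 to 5%, requiring a second, confirming crossing left 8 to 55% apparent slowing with a 6-month window.

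Finally, FVC is secondary in a 10-subject pilot, Section 2 speaks only of early evidence, the synopsis leaves efficacy to a randomized trial, and Section 8 promises a detailed SAP. All of this limits the severity. None of it changes the Section 3.2 wording or defines the window.

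**Conclusion.** The concern holds in this form: the Section 8 slope comparison cannot determine whether pirfenidone slows FVC decline, because its expected value under no drug effect is not known from the plan. Under the assumed declines and visit noise, an inert drug shows about 6 to 57% apparent slowing with a 6-month window and about -50% to +30% with a 12-month window. The sizes rest on those assumptions, and the simulations behind these ranges let every subject complete follow-up. The conclusion rests only on the document facts: entry on a fall in FVC, no scheduled pre-drug FVC, an undefined window and no control arm. A window chosen after seeing the data could move the result either way. This should be corrected, but it does not touch the primary tolerability and tacrolimus outcomes.

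**What to change.** 1. **Section 3.2:** reword as: To describe the course of FVC and of CT fibrosis scores during pirfenidone treatment in subjects with RCLAD.
2. **Section 8 or the SAP, before the data are analysed:** state the pre-drug window and minimum number of values, whether the qualifying value is used, and the slope model, including how a stable phase before onset is treated.
3. **Reporting:** give pre-drug and on-drug slopes with confidence intervals, with and without the qualifying value. Make no before/after test and no claim of slowing attributed to the drug. Neither display is free of bias; the gap between them shows how far the result depends on that one value.
4. **Optional:** if comparable untreated RCLAD patients exist at the site, show their slope change under the same criteria and index date, as descriptive context only. The documents do not show that such patients exist. Differences between groups, and selection of patients who survive to the index date, would remain, so the bias cannot be said to cancel.

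Cost: items 1 to 3 are text changes, with no new patients or visits. The downside is that the secondary objective becomes descriptive. Item 4 adds a retrospective data pull.
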